6.4.4 Investigator’s Global Assessment (IGA mod 2011)

The IGA mod 2011 will be conducted for overall psoriatic disease as indicated in [Table 6-1](#). It is recommended that the same evaluator conducts the assessment throughout the study wherever possible.

Subjects require an IGA mod 2011 score at Randomization of 3 or 4 in order to participate in the study. Based on this scale, a subject will be considered as an IGA 0 or 1 responder if they achieve a score of 0 or 1, and improve by at least 2 points on the IGA scale at a given time point compared to their score at Randomization (Baseline).

The IGA mod 2011 rating scale for overall psoriatic disease is shown in [Table 6-3](#).

The IGA mod 2011 used in this study is static, i.e. it refers exclusively to the subject’s disease state at the time of the assessments, and does not attempt a comparison with any of the subject’s previous disease states, whether at baseline or at a previous visit.

The IGA mod 2011 score will be recorded in the eCRF.

Table 6-3 IGA mod 2011 rating scale

Score	Short description	Detailed description
0	Clear	No signs of psoriasis. Post-inflammatory hyperpigmentation may be present
1	Almost clear	Normal to pink coloration of lesions; no thickening; no to minimal focal scaling
2	Mild disease	Pink to light red coloration; just detectable to mild thickening; predominantly fine scaling
3	Moderate disease	Dull bright red, clearly distinguishable erythema; clearly distinguishable to moderate thickening; moderate scaling
4	Severe disease	Bright to deep dark red coloration; severe thickening with hard edges; severe / coarse scaling covering almost all or all lesions

NOTE: Involvement of the nails is not part of the assessment.

6.4.5 Health-related quality of life (HRQoL)

The impact of psoriasis on various aspects of the subject's health-related quality of life (HRQoL) will be assessed by the following validated instrument which will be performed at the scheduled study visits as indicated in [Table 6-1](#):

- Dermatology Life Quality Index (DLQI)

The quality of life assessment should be completed by the subject prior to being seen by the study physician (Investigator or qualified site staff) who will perform the Investigator assessments.

The subject should be given sufficient space and time to complete the paper questionnaire. The study coordinator should check the questionnaire for completeness and encourage the subject to complete any missing responses.

Before the subject's clinical examination, the Investigator should review the completed questionnaire for responses that may indicate potential AEs or SAEs. If AEs or SAEs are confirmed, the Investigator must record the events as per instructions given in [Section 7](#) of the protocol.

Investigators should not encourage subjects to change the responses reported in the completed questionnaire.

A copy of the DLQI is provided in Section 13 ([Appendix 5](#)).

6.4.5.1 Dermatology Life Quality Index (DLQI)

The Dermatology Life Quality Index (DLQI) is a 10-item general dermatology disability index designed to assess health-related quality of life in adult subjects with skin diseases such as eczema, psoriasis, acne, and viral warts ([Finlay and Khan, 1994](#)). The measure is self-administered and includes domains of daily activities, leisure, personal relationships, symptoms and feelings, treatment, and work/school. The measure is widely used; it has been tested across 32 different skin conditions and is available in 55 languages. The recall period is the last week, and the instrument requires 1 to 2 minutes for completion.

Each item has four response categories, ranging from 0 (not at all) to 3 (very much). "Not relevant" is also a valid response and is scored as 0. The DLQI total score is a sum of the 10 questions. Scores range from 0 to 30 and higher scores indicate greater health-related quality-of-life impairment. Additionally, each subscale of the DLQI may be analyzed separately.

The DLQI questionnaire (date of publication 1994) will be completed by the subject as indicated in [Table 6-1](#).

6.4.6 Appropriateness of efficacy assessments

The primary efficacy assessment is aortic vascular inflammation measured by FDG-PET/CT, an important imaging biomarker and surrogate marker for future vascular risk. FDG-PET/CT is

reliable and predictive of future vascular events independent of other cardiovascular biomarkers, and improves rapidly (i.e., within four weeks) with interventions known to reduce vascular risk (i.e., statins). It is increasingly used as a surrogate marker for novel agents being studied in FDA regulated trials assessing novel strategies for CV risk reduction. Alternative assessments such as carotid IMT and MRI-based measures of wall thickness change only slowly and thus would require longer term trials in which use of placebo would not be feasible. Secondary efficacy assessments include biomarkers that are well established markers of inflammation and cardiovascular risk.

The PASI score is a standard and validated measurement for chronic plaque psoriasis.

The IGA mod 2011 scale has been developed by Novartis in collaboration with health authorities, in particular the FDA. It is based on the previous version of the scale which was used in the Phase II secukinumab studies. In the modified scale, the two “very severe” and “severe” categories have been condensed into a single category of “severe”, and the explanations/descriptions of the points on the scale have been improved to ensure appropriate differentiation between the points.

6.5 Safety

All blood draws and safety assessments must be performed prior to study treatment administration. Appropriate safety assessments (e.g., evaluation of AEs and SAEs including injection site reactions) should be repeated after dosing with study treatment.

Safety assessments will be performed as indicated in [Table 6-1](#):

- Evaluation of all AEs and SAEs (including injection site reactions and occurrence of infections)
- Physical examination
- Vital signs
- Height and weight
- Laboratory evaluations
 - Hematology
 - Clinical chemistry
 - Viral serology
- Pregnancy and assessments of fertility.

6.5.1 Physical examination

A complete physical examination will be performed by a professionally trained physician or health professional licensed to perform physical examinations, and listed on FDA Form 1572. The physical examination, including general appearance, will be performed at the scheduled study visits as indicated in [Table 6-1](#).

If indicated, based on medical history and/or symptoms, additional exams may be performed at the discretion of the Investigator/qualified site staff.

If possible, assessments for an individual subject should be performed by the same Investigator/qualified site staff throughout the study.

Information for all physical examinations must be included in the source documentation at the study site. Significant findings that are present prior to the subject signing informed consent must be included in the Medical History eCRF. Significant findings made after the signing of the informed consent which meet the definition of an AE must be recorded in the subject's Adverse Event eCRF ([Section 7](#)).

6.5.2 Vital signs

Vital signs (including blood pressure and pulse measurements) will be assessed at scheduled study visits as indicated in [Table 6-1](#).

After the subject has been sitting for at least five minutes, with back supported and both feet placed on the floor, systolic and diastolic blood pressure (BP) will be measured using a validated device with an appropriately sized cuff. In case the cuff sizes available are not large enough for the subject's arm circumference, a sphygmomanometer with an appropriately sized cuff may be used. The BP measurement will be recorded in the Vital Signs eCRF.

If possible, assessments should be performed by the same site staff throughout the study.

[figure not shown]
Normal blood pressure will be defined as a systolic pressure of 90 to <120 mmHg, and a diastolic blood pressure of 60 to <80 mmHg under the measurement conditions outlined above. Notable blood pressure will be hypertension (systolic blood pressure of ≥ 140 mmHg and/or diastolic blood pressure of ≥ 90 mmHg) or hypotension (systolic blood pressure of <90 mmHg and/or a diastolic blood pressure of <60 mmHg). A blood pressure indicative of prehypertension (systolic blood pressure of 120 to <140 mmHg and/or diastolic blood pressure of 80 to <90 mmHg) will not be regarded as notable ([Chobanian et al 2003](#)).

A normal pulse rate will be defined as a rate of 60 to 100 beats per minute (bpm) under the measurement conditions outlined above. Notable pulse rates are a rate below 60 bpm (bradycardia) or above 100 bpm (tachycardia).

Whether action needs to be taken to address notable vital signs values will be decided by the Investigator, taking into account the overall status of the subject. No specific action is foreseen as part of the study protocol.

6.5.3 Height and weight

Height and body weight (in indoor clothing but without shoes) will be measured at scheduled study visits as indicated in [Table 6-1](#). If possible, body weight assessments should be performed using the same scale throughout the study.

6.5.4 Laboratory evaluations

A central laboratory will be used for analysis of all specimens collected. Details on the collection, shipment of samples, and reporting of results by the central laboratory will be provided to Investigators in the Laboratory Manual.

Refer to the Laboratory Manual for identification of laboratory reference range values, notable values, and the schema for notification of site staff and Novartis for out of range values.

Section 13 ([Appendix 1](#)) shows the expanded laboratory ranges and the clinically notable abnormalities of key laboratory tests.

6.5.4.1 Hematology

Hemoglobin, hematocrit, red blood cell count, white blood cell count with differential (neutrophils including bands, lymphocytes, monocytes, eosinophils, basophils) and platelet count will be measured at scheduled study visits as indicated in [Table 6-1](#).

6.5.4.2 Clinical chemistry

Blood urea, creatinine, total bilirubin, ALT (SGPT), AST (SGOT), GGT, alkaline phosphatase, and hemoglobin A1c (HbA1c) will be measured at scheduled study visits as indicated in [Table 6-1](#); HbA1c will be measured at screening only.

6.5.4.3 Fasting laboratory evaluations

Fasting (8 hour duration with water *ad libitum*) laboratory tests will be performed at screening and will include:

- Plasma glucose

6.5.4.4 Viral serology

[figure not shown]
Viral serology will be performed at screening and will include:

- Hepatitis screening: Hepatitis B surface antigen (HBsAg); Hepatitis C virus antibody (HCVAbs)
- HIV screening: HIV 1/2

To be eligible for randomization, subjects must have “non-reactive” serology results at screening.

6.5.5 Pregnancy and assessments of fertility

At the Screening visit, a serum β -hCG pregnancy test will be performed in all women except those who are sterile or post-menopausal. Any woman with a confirmed positive pregnancy test during screening is not eligible for randomization.

Starting at Visit 2/Baseline, all women except those who are sterile or post-menopausal will have a local urine pregnancy test at scheduled study visits as indicated in [Table 6-1](#).

A positive urine pregnancy test during the study requires immediate interruption of study treatment until serum β -hCG is performed and found to be negative. If the serum β -hCG test is positive, the subject must be discontinued from the study as described in [Section 5.5.9](#).

6.5.6 Appropriateness of safety measurements

The safety assessments selected for this study are reliable and standard measures for a biologic immunomodulating agent in adult patients with psoriasis.

6.6 Other assessments

No additional tests will be performed on subjects entered into this study.

7 Safety monitoring

7.1 Adverse events

An adverse event (AE) is any untoward medical occurrence (i.e., any unfavorable and unintended sign [including abnormal laboratory findings], symptom or disease) in a patient or clinical investigation subject *after providing written informed consent* for participation in the study. Therefore, an AE may or may not be temporally or causally associated with the use of a medicinal (investigational) product. Study treatment includes the study drug under evaluation and the comparator treatment or placebo that is given during any phase of the study. Medical conditions/diseases present at the time of screening are only considered AEs if they worsen after the subject has signed informed consent.

For all subjects who sign informed consent and who are randomized into the Double-blind Treatment Period of the study will have all adverse events that occur **after informed consent is signed** recorded on the Adverse Event CRF.

The occurrence of adverse events should be sought by non-directive questioning of the subject at each visit during the study. Adverse events also may be detected when they are volunteered by the subject during or between visits or through physical examination, laboratory test, or other assessments.

Abnormal laboratory values or test results constitute adverse events only if they fulfill at least one of the following criteria:

- they induce clinical signs or symptoms;
- they are considered clinically significant; and/or
- they require therapy.

Clinically significant abnormal laboratory values or test results should be identified through a review of values outside of normal ranges/clinically notable ranges, significant changes from baseline or the previous visit, or values which are considered to be non-typical in subject with underlying disease. Investigators have the responsibility for managing the safety of individual subject and identifying adverse events. Alert ranges for labs and other test abnormalities are included in [Appendix 1](#).

Adverse events should be recorded in the Adverse Events eCRF under the signs, symptoms or diagnosis associated with them, accompanied by the following information:

- Severity grade
 - mild: usually transient in nature and generally not interfering with normal activities
 - moderate: sufficiently discomforting to interfere with normal activities
 - severe: prevents normal activities
- Relationship to the study treatment
- Duration (start and end dates or if continuing at final exam)
- Whether it constitutes a serious adverse event (SAE - See [Section 7.2](#) for the definition of SAE)
- Action taken regarding study treatment
- Concomitant medication(s) taken or non-drug therapies given
- Outcome.

Once an adverse event is detected, it should be followed until its resolution or until it is judged to be permanent. An assessment should be made at each visit (or more frequently, if necessary) of any changes in severity, the suspected relationship to the study treatment, the interventions required to treat it, and the outcome.

Information about common side effects already known about the study drug can be found in the Investigator Brochure (IB) or will be communicated between IB updates in the form of Investigator Notifications (INs). This information will be included in the subject informed consent and should be discussed with the subject during the study as needed.

7.2 Serious adverse events

7.2.1 Definition of SAE

An SAE is defined as any adverse event (appearance of (or worsening of any pre-existing) undesirable sign(s), symptom(s) or medical conditions(s) which meets any one of the following criteria:

- is fatal or life-threatening
- results in persistent or significant disability/incapacity
- constitutes a congenital anomaly/birth defect

- requires inpatient hospitalization or prolongation of existing hospitalization, unless hospitalization is for:
 - routine treatment or monitoring of the studied indication, not associated with any deterioration in condition (specify what this includes)
 - elective or pre-planned treatment for a pre-existing condition that is unrelated to the indication under study and has not worsened since signing the informed consent
 - treatment on an emergency outpatient basis for an event not fulfilling any of the definitions of a SAE given above and not resulting in hospital admission
 - social reasons and respite care in the absence of any deterioration in the subject's general condition
- is medically significant, i.e. defined as an event that jeopardizes the subject or may require medical or surgical intervention.

All malignant neoplasms will be assessed as serious under “medically significant” if other seriousness criteria are not met.

Life-threatening in the context of a SAE refers to a reaction in which the subject was at risk of death at the time of the reaction; it does not refer to a reaction that hypothetically might have caused death if more severe (see Annex IV, ICH-E2D Guideline).

Medical and scientific judgment should be exercised in deciding whether other situations should be considered serious reactions, such as important medical events that might not be immediately life threatening or result in death or hospitalization but might jeopardize the subject or might require intervention to prevent one of the other outcomes listed above. Examples of such events are intensive treatment in an emergency room or at home for allergic bronchospasm, blood dyscrasias or convulsions that do not result in hospitalization or development of dependency or abuse (see Annex IV, ICH-E2D Guideline).

Any suspected transmission via a medicinal product of an infectious agent is also considered a serious adverse reaction.

All AEs (serious and non-serious) are captured on the eCRF, SAEs also require individual reporting to DS&E as per Section 7.2.2.

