### **Serious Adverse Event (SAE)**

Number and percentage of patients with serious adverse events, regardless of study drug relationship, will be presented by primary system organ class and preferred term. Primary system organ classes will be sorted alphabetically and, within each primary system organ class, the preferred terms will be sorted in descending order of frequency.

If a patient reported more than one adverse event with the same preferred term, the adverse event will be counted only once. If a patient reported more than one adverse event within the same primary system organ class, the patient will be counted only once at the system organ class level.

All SAEs will be listed.

Adverse events and serious adverse events up to and including the Week 12 visit will be included in the database for the analysis at the primary analysis time point (Week 12).

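### The last SAE criterion in Protocol 7.2.1 omits the limit on intervention that a later paragraph of the same section applies, so one reportable classification has two different tests

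*Protocol*

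**What the plan says.** Protocol 7.2.1 defines an SAE as an adverse event "which meets any one of the following criteria". The last criterion in the list is that the event "is medically significant, i.e. defined as an event that jeopardizes the subject or may require medical or surgical intervention". The bullet ends there.

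The third paragraph after the list says that "Medical and scientific judgment should be exercised in deciding whether other situations should be considered serious reactions". It describes important medical events as ones that "might jeopardize the subject or might require intervention to prevent one of the other outcomes listed above", gives severe examples (such as convulsions or blood dyscrasias without admission) and points to an ICH guideline.

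In the same list, the first hospitalization exception contains an unfilled template prompt: "not associated with any deterioration in condition (specify what this includes".

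Protocol 7.1 refers to Section 7.2 for the SAE definition when a site records whether an event is serious. Protocol 7.2.2 requires every SAE to be reported within 24 hours. SAP 2.8.1 includes adverse events in the summaries up to 7 days after the last dose, but SAEs up to 30 days. For SAEs the SAP adds: "Number and percentage of patients with serious adverse events, regardless of study drug relationship, will be presented", by system organ class and preferred term.

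**The concern.** The bullet is worded as a definition and is sufficient on its own. Its second limb asks only whether medical or surgical intervention may be needed. Many ordinary adverse events in a 52-week psoriasis trial meet that test, for example a candida infection given an antifungal. The later paragraph asks a different question: whether intervention is needed to avert death, hospitalization, disability or another listed outcome. A site that applies the bullet alone is following the protocol, and so is a site that relies on the paragraph, yet the two can classify the same event differently.

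The seriousness flag decides whether an event enters the SAE table, whether it must be reported within 24 hours, and whether it is summarised under the 30-day or the 7-day window. For screening failures it also decides whether the event reaches the eCRF at all (Protocol 6.1). Safety and tolerability is a stated secondary objective. Protocol 8.4 and 8.5 require no monitoring or adjudication committee, so neither would standardise the flag.

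**Working it through.** No figure in the documents depends on this wording, so there is none to reproduce. The check is a comparison of texts, followed by an illustration on assumed inputs.

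**Text comparison**

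1. *How the criteria combine.* One criterion is enough ("which meets any one of the following criteria"), so the last bullet can make an event serious alone.
2. *The bullet's test.* The event jeopardizes the subject, or intervention may be required. No purpose is stated for the intervention.
3. *The paragraph's test.* The event might jeopardize the subject, or intervention might be required to prevent another listed outcome. The purpose is stated.
4. *Does the paragraph limit the bullet?* Not formally. It is introduced as judgment on situations other than those listed ("Medical and scientific judgment should be exercised in deciding whether other situations should be considered serious reactions").
5. *Does Protocol 7.1 settle it?* Only indirectly. There, one of the tests for whether an abnormal laboratory value is an adverse event at all is that "they require therapy". Under the literal bullet, every laboratory event recorded on that ground would also be serious. Protocol 7.1 further lists "Concomitant medication(s) taken or non-drug therapies given" among the items recorded for an adverse event. That field applies to serious and non-serious events alike, so it does not show that treated events are meant to be non-serious.

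The two tests therefore differ for any event that may need treatment but does not jeopardize the subject and whose treatment is not meant to avert a listed outcome.

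**Illustration of size**

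From the documents: N = 84 subjects (Protocol 3.1 and 9.7). Assumed, because the documents give no values:

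- s = proportion with an SAE on the narrow test, 2% to 5%
- t = proportion with any adverse event needing treatment, 10% to 50%
- f = share of subjects at sites that read the bullet literally, 0 to 1

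Subjects with an SAE = 84 × [s + f × (t − s)].

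- f = 0: 84 × 0.02 = 1.7 to 84 × 0.05 = 4.2.
- f = 0.5, lowest case (s = 2%, t = 10%): 84 × (0.02 + 0.5 × 0.08) = 84 × 0.06 = 5.0.
- f = 0.5, highest case (s = 5%, t = 50%): 84 × (0.05 + 0.5 × 0.45) = 84 × 0.275 = 23.1.
- f = 1: 84 × 0.10 = 8.4, 84 × 0.30 = 25.2 and 84 × 0.50 = 42.0 for t = 10%, 30% and 50%.

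The smallest increase at f = 0.5 is with s = 5% and t = 10%: 84 × (0.05 + 0.5 × 0.05) = 6.3, against 4.2. The range from f = 0 to f = 1 runs from no inflation to half the trial. It shows only that the count is sensitive to the reading; it does not estimate what will happen.

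**The case against.** The strongest reply is that Section 7.2.1 largely answers itself. The bullet opens by requiring medical significance. The paragraph supplies the limiting clause, severe examples, a guideline reference and an instruction to use judgment. The rule assigning malignancies to the medically significant category also suggests a narrow intent, since it would hardly be needed if any treatable event already qualified. An investigator who reads the whole section will probably apply the narrower test. This stands as evidence of intent, and it is why the texts are better called inconsistent than contradictory. It does not repair the bullet, which is the operative criterion.

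The impact is also bounded. SAEs are summarised descriptively, with no planned test. All are listed and tabulated by preferred term, so a trivial event called serious would be visible. The general adverse event table does not depend on seriousness except between 7 and 30 days after the last dose. This stands too.

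Three stronger readings may tempt a reader, and the documents do not support them.

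- *Inflation would be uneven across sites.* Different readings are possible, but neither document has evidence of site practice. If every site read the bullet literally, there would be inflation without unevenness.
- *Inflation would be unequal between arms.* Protocol 3.6 gives higher rates on secukinumab for nasopharyngitis, upper respiratory infection and candida: 11.4 + 2.5 + 1.2 = 15.1%, against 8.6 + 0.7 + 0.3 = 9.6% on placebo. Per 42 subjects that is 6.3 against 4.0. These are incidences, not treated-event rates. The figures need no overlap, treatment of every event and a literal reading at every site. Assessors are blinded to assignment (Protocol 5.4), so any difference would follow a real difference in infections. An imbalance is conceivable but not shown.
- *The bullet conflicts with the exception for emergency outpatient treatment.* It does not. That exception sits under the hospitalization criterion and refers back to criteria listed before it; the medically significant bullet comes after.

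**Conclusion.** The point holds as an error of wording with a practical consequence. The last SAE criterion lacks the limit that the same section applies later, so the protocol gives two tests for one reportable classification. Followed literally, the bullet would make routinely treated adverse events serious. That risks inflating SAE counts and percentages, the number of 24-hour reports, and the set of events summarised under the 30-day window.

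The text comparison rests on no assumption. The size does: SAE and treated-event rates and the share of literal-reading sites are all assumed, so the size must be called unknown. The primary efficacy analysis and the sample size are unaffected. The unfilled prompt in the hospitalization exception is a separate editorial slip.

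**What to change.** Extend the intervention limb of the last bullet in Protocol 7.2.1 with the purpose clause that closes "might jeopardize the subject or might require intervention to prevent one of the other outcomes listed above", so that bullet and paragraph state the same test. Complete or delete the template prompt in the first hospitalization exception.

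If the SAE report form records which criterion an event met, query before the Week 12 lock, while still blinded, every event called serious only under this criterion. Protocol 7.1 lists only whether an event is serious, and the form itself is not in the documents, so check this first. The query can correct events called serious too readily; it cannot find SAEs that were missed.

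The cost is one clause in an amendment or site clarification letter, one editorial correction and a few data queries. Design, sample size and efficacy analysis do not change.
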